14.1.2 Principal strata analysis

A principal strata analysis will be performed where only patients without protocol violations will be analyzed according to Section 14.1.1. In particular patients who did not comply with the dosing scheme but continued the study will be excluded from the analysis.

14.2 The HS endpoint

One of the key secondary objectives is to evaluate the effect of SOBI003 on HS levels in CSF.

To evaluate the effect of SOBI003 on HS levels in CSF linear models are used to model the change from baseline in HS levels as dependent variable, for both logged HS levels and untransformed HS levels, and baseline level and age as continuous covariates, and accumulated dose (including the FIH study) as covariate and sex as factor. The analyses are conducted for each assessment time point: baseline, week 52 and 104.

In addition, linear analyses with HS levels, both logged HS levels and untransformed HS levels, in CSF, serum and urine, as dependent variable, and baseline level and age as continuous covariates, and accumulated dose as covariate and sex as factor will be performed across all assessments (including the FIH study), with assessment as a repeated factor.

For the purpose of the multiple testing procedure (see Section 14.3), the linear repeated measures analysis with untransformed HS in CSF levels will be used, identical to the DQ analysis with the exception of the treatment factors.

The time effect is used to judge the HS level change in CSF. The null hypothesis of no change will be tested with a significance test for the time-effect in the first step of the multiple testing procedure (see Section 14.3). The difference between 104 weeks and baseline will be used as the contrast of interest for the test.

The evaluation of the effect of SOBI003 on HS levels in serum and urine will utilize the same models as mentioned above for HS levels in CSF.

The HS levels including change from baseline will also be summarized using descriptive statistics: n, mean, standard deviation (SD), standard error of the mean (SE), median, minimum and maximum. The HS change from baseline will also be presented as percentages. In addition, HS levels, change from baseline in HS levels and change from baseline in HS levels expressed as percentages will be presented in figures: by subject as well as mean graphs.

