Furthermore, a principal strata analysis will be performed where only patients without protocol violations will be analyzed according (see Section 14.1.2). In particular patients who did not comply with the dosing scheme but continued the study will be excluded from the analysis. Thus the principal strata will be approximated by the clinical per protocol subset of FAS.

7 Sample size determination

7.1 Change from baseline in DQ score and in HS levels in CSF at 104 weeks

All patients completing the FIH study will be offered to continue into this extension study and the number of patients in the extension study is thus not based on statistical grounds.

However, the 14 patients in the natural history study that will be used as an external control group had a mean baseline DQ of 58.9 points and declined with a mean of 30.4 (SD=12.1) DQ points during 104 weeks. Therefore, assuming very high likelihood of showing significant decrease in HS (with baseline mean of 5.2, std 1.8, correlation of 0.1 and a decrease of 80 % the power is 99 %), with 9 patients treated with SOBI003, the power to demonstrate an improvement in cognitive function is at least 80 % if the decline is reduced from 30.4 to 9.8 DQ points (SD=13.0) and the reduction is homogeneous across age.

8 Analysis sets

The following analysis sets will be used in the statistical analyses and exploration of data.

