14.1 The DQ endpoint

One of the key secondary objectives is to assess the effect of SOBI003 on neurocognition, as compared to untreated MPS IIIA patients from a NH control. The key endpoint related to this

objective is the change from baseline in DQ of neurocognitive development at 104 weeks of treatment, and will be estimated by a model based contrast.

To address the efficacy objective, a repeated measure analysis will be utilized where DQ is the response variable and time, baseline age, time*baseline age and treatment*time are fixed effects and the dependency between observations within the same patient is represented by an unstructured variance-covariance matrix.

The time window is two weeks, i.e., if the assessment is more than two weeks too early or more than two weeks too late, then the DQ is set to missing for that assessment.

In the NH study, a simple linear regression model was used, i.e. with DQ as the response variable and the age of the child as dependent variable (Shapiro et al 2016). As the aim in this clinical development program is to demonstrate that treatment with SOBI003 is efficacious and the effect of treatment is dependent on the time the patient has been treated, this model needs to be adopted so that time and baseline age are factors rather than the actual age of the child (which is the sum of the baseline age and the time in study). The results from the NH study suggest that the decline in DQ is not linear across all ages, and an interaction term time*baseline age is planned to be included in the model to allow for such a non-linearity. Also an unstructured variance-covariance matrix is planned to be used to account for the dependency between observations within the same patient. As a further justification for the model, it should be noted that time, baseline age and time*baseline age are all significant factors in the NH study.

To represent the treatment effect without constraint to a specific relation across visits, a term treatment*time is planned to be included in the model. This effect is used to judge the treatment effect. The null hypothesis of no treatment effect will be tested with a significance test for the treatment*time-effect in the second step of the multiple testing procedure (see Section 14.3). The difference between 104 weeks and baseline will be used as the contrast of interest for the test.

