14.3 Multiple comparison procedure

A hierarchical approach will be used for the key secondary co-endpoints.

The primary analysis will be based on a 2-sided test using a significance level of 0.05. A stepwise sequential testing procedure will be used to ensure a multiple level of significance of 0.05.

- 1st step: The null hypothesis of no difference between the treatments with respect to the reduction from baseline HS in CSF at 24 months will be tested using a significance level of 0.05. If the null hypothesis is rejected, then it will be concluded that SOBI003 reduces HS. Furthermore, the 2nd step of the sequential testing procedure will be performed.
- 2nd step: The null hypothesis of no difference between the treatments with respect to the change in DQ score at 24 months will be tested using a significance level of 0.05. If the null hypothesis is rejected, it will be concluded that Sobi 003 improves cognitive function as compared to untreated patients.

This multiple comparison procedure controls that the multiple level of significance is no more than 5 %.

Formally, the second confirmatory step will only be valid after the 1st step has been successfully met.

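### The gatekeeping CSF HS test does not say at which baseline age it is evaluated; coded literally with uncentred age, it tests the change at age zero and can fail despite an 80% reduction

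*SAP*

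**What the plan says.** Three parts of the SAP combine here.

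- **Model for DQ (SAP 14.1).** The repeated measures model has DQ as response; "time, baseline age, time*baseline age and treatment*time are fixed effects", with an unstructured covariance matrix. The interaction with baseline age is justified by the pattern of DQ decline in the natural history data.
- **Model and test for HS (SAP 14.2).** For the multiple testing procedure, untransformed CSF HS is analysed with a model "identical to the DQ analysis with the exception of the treatment factors". The null hypothesis of no change "will be tested with a significance test for the time-effect in the first step", and the Week 104 minus baseline difference is named as the contrast. No age is attached to it, and centring is not mentioned.
- **Hierarchy (SAP 14.3).** The analysis "will be based on a 2-sided test using a significance level of 0.05". The DQ step is formally valid only if the HS step succeeds.

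The protocol (9.4.4.1 and the synopsis) also makes the HS model the same as the DQ model apart from treatment. Its DQ model, however, has visit, visit-by-treatment and baseline age as a covariate, with no time*baseline age term. The HS estimand in SAP 6 and protocol 9.3 is the decline in all patients who meet the entry criteria.

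**The concern.** Removing treatment*time from the SAP's DQ model leaves time, baseline age and time*baseline age for HS. In such a model the change between visits depends on age. The coefficients of the time term alone describe the change where age equals zero. With age in months and uncentred, that is an extrapolation to birth.

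The SAP's wording invites this coding. In 14.1 a named model term, treatment*time, is the effect used to judge treatment. In 14.2 the time effect is used in the same way to judge HS. For DQ the wording is harmless, because the main DQ model has no treatment*time*age term and its contrast is the same at every age. Carried over to HS, it is no longer harmless.

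What is at stake is the gate. A Step 1 failure caused by extrapolation would close off the only formal DQ comparison, although HS had fallen as planned. It would also not answer the question set by the estimand.

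**Working it through.** **Inputs**
- SAP 7.1 (protocol 9.1): 9 treated patients, and HS "with baseline mean of 5.2, std 1.8, correlation of 0.1 and a decrease of 80 % the power is 99"%.
- SAP 14.3: two-sided 0.05.
- Not in the documents: the ages of the treated patients (varied below), the Week 104 SD (two cases below) and the degrees-of-freedom method (n − 2 used for the interaction model). Complete data and the same true HS change at all ages are assumed.

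**Step 1. Reproduce the stated 99%.** Change = 0.8 × 5.2 = 4.16. If the SD is 1.8 at both visits, SD of change = √(2 × 1.8² × (1 − 0.1)) = 2.415. For a paired t-test with n = 9 and 8 df, the noncentrality is 4.16 / (2.415/√9) = 5.17 and power is 99.4%. The plan's figure is reproduced, and it is the power for a mean change.

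**Step 2. SAP model, contrast at the mean age.** With complete data and unstructured covariance, the Week 104 minus baseline contrast is the fitted value from regressing each patient's change on baseline age. At the mean age the SE is still 2.415/3 = 0.805, now with 7 df. Power is 99.2%; a simulation of 20,000 runs also gave 99.2%.

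**Step 3. SAP model, contrast at age 0.** With m and s the mean and SD of baseline age,

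SE₀ = SD of change × √(1/n + m² / ((n − 1) s²)).

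For m = 42 and s = 17 months: SE₀ = 2.415 × √(1/9 + 1764/(8 × 289)) = 2.258. This is 2.80 times 0.805. The noncentrality is 4.16/2.258 = 1.84, and power with 7 df is 36%.

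Power at age 0 by assumed ages, n = 9, SD of change 2.415:

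| Mean age (months) | SD of age (months) | SE inflation | Power |
|---|---|---|---|
| 30 | 20 | 1.88 | 66% |
| 48 | 20 | 2.73 | 37% |
| 42 | 17 | 2.80 | 36% |
| 30 | 12 | 2.83 | 35% |
| 48 | 12 | 4.36 | 18% |

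Evenly spaced ages give a similar picture: 12–72 months 46% (simulation 47%), 12–48 months 36%, 24–72 months 28%, 24–60 and 12–30 months 22%, 36–72 months 16%. An extreme two-cluster spread (four patients at 12 months, one at 42, four at 72) gives 70%.

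**Step 4. Sensitivity**
- *Smaller SD of change.* If the Week 104 SD also falls by 80%, to 0.36, SD of change = √(1.8² + 0.36² − 2 × 0.1 × 1.8 × 0.36) = 1.80. The mean/SD grid then gives 28% to 88%, the evenly spaced ranges 24% to 70%, and the two-cluster spread 91%.
- *12 patients, SD of change 2.415.* The mean/SD grid gives 24% to 82%; power at the mean age is above 99.9%.
- *Protocol model, no interaction.* The contrast does not depend on age, and power is 99.4% as in Step 1.

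**The case against.** The strongest reply is that the SAP never says age zero. SAP 14.2 names the difference between Week 104 and baseline as the contrast. SAP 14.1 speaks of a model-based contrast, and SAP 9 promises estimated means and differences with confidence intervals. A least-squares-mean difference at the mean age fits all of this, suits the all-patient estimand, and agrees with the 99% power figure. This stands. A reader might infer that the gatekeeping test, as planned, does evaluate HS at age zero. The documents do not support that; they leave the evaluation point open.

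A reader might also take the fault to run through both documents. It does not: the protocol's model has no time*baseline age term, so its time contrast is the same at every age. What the documents do show is that the two models differ.

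The magnitude is illustrative. The 12 to 72 month range describes the natural history controls, not the treated patients, so it cannot be stated as fact that no treated patient is near age zero. The SD of change of 2.415 assumes equal SDs at both visits.

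Finally, the primary objective is safety, the sample size is not statistically based, and HS is also summarised and modelled in other ways. That limits the consequences for the trial as a whole. It does not repair the gate, because only this test releases the formal DQ comparison. Nor is the ambiguity harmless: two programmers following SAP 14.2 could run tests with very different power on the same data, and choosing between them after seeing results would undermine the error control claimed in SAP 14.3.

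**Conclusion.** The point holds in conditional form. SAP 14.1 and 14.2 together put time*baseline age in the Step 1 HS model and name the time effect as the test, without centring age or fixing the age of the contrast. Coded literally with uncentred age, the test targets the change at age 0 and can fail despite a true 80% reduction. Power would be about 18% to 66% over mean ages of 30 to 48 months and SDs of 12 to 20 months (16% to 46% for the evenly spaced ranges), against 99% at the mean age. With the smaller SD of change the same grid gives 28% to 88%. All these figures rest on assumed ages, 9 patients and complete data.

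It should not be read as showing that the planned test must fail, or that the main DQ contrast is affected. The DQ sensitivity model with time*treatment*baseline age (SAP 14.1.1) does raise the same question about where its contrast is evaluated.

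**What to change.** Before database lock:

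1. In SAP 14.2, define Step 1 as the Week 104 minus baseline difference in least-squares means at the mean baseline age of the treated patients; centring baseline age at that mean is equivalent. Alternatively, drop time*baseline age from the HS model, as in the protocol. The SAP's rationale for the interaction concerns DQ decline only.
2. Reconcile the repeated measures models in protocol 9.4.4.1 and SAP 14.1, and record the reason for any difference.
3. In SAP 14.1.1, centre baseline age, or state the age of the contrast, for the model with the triple interaction.

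The cost is one sentence in SAP 14.2, a line in 14.1.1 and a note reconciling the models. Nothing changes in data collection or conduct. Either option in item 1 brings Step 1 back to the stated power: 99.2% with the interaction kept, 99.4% without it.

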14.2.1 Sensitivity analyses of the HS endpoint

In order to assess the sensitivity of the model, the HS model described in 14.2 will

- Only use non-missing values, i.e., no imputations will be performed

An addition sensitivity analysis will be a tipping point analysis: All observed HS values in the study are substituted for missings.

14.3 Multiple comparison procedure

A hierarchical approach will be used for the key secondary co-endpoints.

The primary analysis will be based on a 2-sided test using a significance level of 0.05. A stepwise sequential testing procedure will be used to ensure a multiple level of significance of 0.05.

- 1st step: The null hypothesis of no difference between the treatments with respect to the reduction from baseline HS in CSF at 24 months will be tested using a significance level of 0.05. If the null hypothesis is rejected, then it will be concluded that SOBI003 reduces HS. Furthermore, the 2nd step of the sequential testing procedure will be performed.
- 2nd step: The null hypothesis of no difference between the treatments with respect to the change in DQ score at 24 months will be tested using a significance level of 0.05. If the null hypothesis is rejected, it will be concluded that Sobi 003 improves cognitive function as compared to untreated patients.

This multiple comparison procedure controls that the multiple level of significance is no more than 5 %.

Formally, the second confirmatory step will only be valid after the 1st step has been successfully met.

14.4 Adaptive Behavior

The adaptive behavior age-equivalent score is determined as the mean of the subdomain age-equivalent scores including the communication, socialization, and daily living skills (thus excluding the motor skills domain).

Adaptive behavior will be analyzed with the same repeated measures model as DQ and described in Section 14.1, but adapted for one group (i.e., no treatment*visit interaction term).

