## STUDY OBJECTIVES

The efficacy analysis will be based on data 2 years after the start of the FIH study ([SOBI003-001](#)), baseline being baseline assessments in the FIH study.

Primary objective:

To assess the long-term safety and tolerability of SOBI003.

Secondary objectives:

The key secondary objectives are:

- To assess the effect of SOBI003 on neurocognition, as compared to untreated MPS IIIA patients from a natural history (NH) control
- To evaluate the effect of SOBI003 on heparan sulfate (HS) levels in CSF

The secondary objectives are:

1. To assess the effect of SOBI003 on adaptive behavior, as compared to untreated MPS IIIA patients from a NH control
2. To assess the effect of SOBI003 on HS levels in serum and urine
3. To assess the effect of SOBI003 on brain magnetic resonance imaging (MRI) abnormalities
4. To assess the effect of SOBI003 on liver and spleen volume
5. To assess the effect of SOBI003 on Quality of Life
6. To assess the effect of SOBI003 on language
7. To assess the effect of SOBI003 on motor function
8. To assess the effect of SOBI003 on sleep pattern
9. To assess the immunogenicity of SOBI003
10. To characterize steady-state pharmacokinetics (PK) of SOBI003 by the use of non-compartmental analysis (NCA)

Exploratory objectives:

The exploratory objectives are:

1. To assess the effect of SOBI003 on adaptive behavior over time.
2. To characterize the PK properties of SOBI003 following repeated administration by the use of population PK analysis

3. To evaluate the PK/PD relationship between SOBI003 concentrations in serum and effect of SOBI003 on HS levels in CSF, serum and urine by the use of population modelling analysis
4. To evaluate the PK/PD relationship between SOBI003 concentrations in serum and CSF, and the effect of SOBI003 on other biomarkers than HS and neuro-cognitive measures by use of population modelling.

As local regulations permit and provided that additional separate caregiver consent is given, the exploratory objectives are also to:

5. Collect and store serum and CSF samples to enable analyses of biomarkers with possible relation to safety, tolerability, immunogenicity, PK and PD of SOBI003, as identified in future

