Immunogenicity is summarized using frequency counts and percentages by dose level and will be evaluated regarding antibody prevalence (pre-existing antibodies), antibody incidence, titer and boosting following dosing, impact on PK and PD.

Adaptive behavior will be analyzed with the same repeated measures model as DQ, but adapted for one group (i.e. no treatment\*visit interaction term).

To assess the PD effect of SOBI003 on MRI, linear models are used to model the change from baseline in MRI as dependent variable for both logged MRI and untransformed MRI, and baseline level and age as continuous covariates, and accumulated dose (including the FIH study) as covariate and sex as factor. The analyses will be conducted for each assessment time point: week 52 and 104.

In addition, linear analyses with MRI levels (both logged MRI levels and untransformed MRI levels), as dependent variable, and baseline level and age as continuous covariates, and accumulated dose as covariate and sex as factor will be performed across all assessments (including the FIH study), with assessment as a repeated factor.

Endpoints relating to other neurocognitive variables, liver and spleen volume, QoL, language, motor function and sleep pattern are summarized using descriptive statistics.

PK results are presented by dose level using descriptive statistics. In addition, results are presented by demographic characteristics, e.g., age-group and bodyweight, as applicable.

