## **7 Investigational plan**

### **7.1 Overall study design and plan**

This is an open, single-arm, multicenter extension study to assess the long-term safety, tolerability and efficacy of SOBI003 in pediatric MPS IIIA patients who previously participated in the FIH study ([SOBI003-001](#)) study. Patients completing the 24-week treatment of the FIH study will be offered to participate in the continuous 80 week treatment period of the extension study. The extension study starts with enrolment at Week 25, giving a total SOBI003

treatment duration of 104 weeks for each patient. Please refer to Figure 1 for an overview of the study design. A recent NH study is used as external control (22) to enable an evaluation of efficacy. Neurocognitive and adaptive behavior data assessed in the extension study at Week 52 and Week 104 following start of treatment will be compared to available NH data within the target study population. The NH population for comparison consists of 14 patients with a rapid progressive MPS IIIA disease and a baseline age of 12 to 72 months.

As the FIH study ([SOBI003-001](#)) has a sequential, ascending, multiple-dose design, the first patients will enter the extension study before the FIH study is completed. When entering the extension study, these patients will receive the highest dose that has been declared safe by the SRC in the ongoing FIH study ([SOBI003-001](#)) study. Patients enrolled in Cohort 1 of FIH study may thus be switched to the dose applied in Cohort 2 or Cohort 3, depending on safety clearance by the SRC. If a patient is initially switched to the dose applied in Cohort 2, the patient may subsequently later be switched to the dose applied in Cohort 3. Depending on recruitment rate in the FIH study ([SOBI003-001](#)) study, a patient enrolled in Cohort 1 may be directly switched to the dose applied in Cohort 3. Upon completion of the FIH study, an analysis aimed at selecting the dose for forthcoming studies will take place. Once the dose has been selected, this dose will be applied to all patients enrolled in the extension study.

[figure not shown]

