## 7.2 Discussion of study design

Patients completing the 24-week, open-label treatment period of the FIH study ([SOBI003-001](#)) study will be offered enrolment into the 80 week extension study SOBI003-002, giving a total SOBI003 treatment duration of 104 weeks (2 years) for each patient.

Although the SOBI003-002 is designed to primarily assess the safety and tolerability of long-term SOBI003 treatment, the inclusion and exclusion criteria have been selected to allow for an efficacy comparison with data from a recent NH study (22).

In very rare and life-threatening diseases such as MPS IIIA alternative designs to a placebo or untreated control are often needed. A position statement by key experts in the field proposes the

use of natural history data instead of formal comparator groups in clinical studies in MPS diseases (24). In the case of treatment of MPS IIIA, no active comparator exists and Sobi does not consider it ethical to withhold a potentially efficient treatment in patients with a rapidly progressive, and life-shortening condition. Data from a recent NH study (22) will therefore serve as control for the studies in the SOBI003 clinical program.

In order to compare SOBI003 treatment with the NH study, comparable patients will be included and the time points for efficacy evaluations and the neurocognitive and behavioral tools used will be identical. The efficacy endpoints in the SOBI003 clinical development program have been selected based on the recommendations in a position statement by key experts in the field, the clinical relevance (24, 25, 26 ) as well as on the endpoints in the NH study (22). The efficacy analysis will be based on data 2 years after the start of the FIH study ([SOBI003-001](#)), baseline being baseline assessments in the FIH study. The choice of treatment duration is based on advice from key clinical experts in the area and the availability of NH data. It is considered long enough to differentiate efficacy of SOBI003 treatment compared to an untreated control.

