#### **9.4.4.2 Secondary endpoints and additional key secondary endpoints**

To assess the PD effect of SOBI003 on HS levels in CSF, serum and urine, linear models are used to model the change from baseline in HS levels as dependent variable, for both logged HS levels and untransformed HS levels, and baseline level and age as continuous covariates, and accumulated dose as covariate and sex as factor. The analyses are conducted for each assessment time point. In addition, linear analyses with HS levels, both logged HS levels and untransformed HS levels, in CSF, serum and urine, as dependent variable, and baseline level and age as continuous covariates, and dose and sex as factors will be performed across all assessments, with assessment as a repeated factor.

Adaptive behavior will be analyzed with the same repeated measures model as DQ, but adapted for one group (i.e. no treatment\*visit interaction term), the SOBI003 group.

PK results are presented by dose level using descriptive statistics. In addition, results are presented by demographic characteristics, e.g., age-group and bodyweight, as applicable.

Immunogenicity is summarized using frequency counts and percentages by dose level. To assess the PD effect of SOBI003 on MRI, linear models are used to model the change from baseline in MRI as dependent variable, for both logged MRI and untransformed MRI, and baseline level and age as continuous covariates, and accumulated dose (including the FIH study) as covariate and sex as factor. The analyses are conducted for each assessment time point i.e. Weeks 52 and 104.

In addition, linear analyses with MRI levels, both logged MRI levels and untransformed MRI levels, as dependent variable, and baseline level and age as continuous covariates, and accumulated dose as covariate and sex as factor will be performed across all assessments (including the FIH study), with assessment as a repeated factor.

Endpoints relating to the neurocognition, adaptive behavior, liver and spleen volume, QoL, language, motor function and sleep pattern are summarized using descriptive statistics.

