4.1 Overall study design and plan

This is an open, single-arm, multicenter extension study to assess the long-term safety, tolerability and efficacy of SOBI003 in pediatric MPS IIIA patients who previously participated in the (FIH) SOBI003-001 study. Patients completing the FIH study will be offered to participate in the extension study. Please refer to Figure 1 for an overview of the study design. A published natural history study (referred to as the NH study in the present document) is used as external control (**Error! Reference source not found.**). Neurocognitive and adaptive behavior data assessed in the extension study at Week 52 and Week 104 following start of treatment will be compared to available natural history data within the target study population. The natural history population for comparison consists of 14 patients with a rapid progressive MPS IIIA disease and a baseline age of 12 to 72 months.

[figure not shown]
As the FIH study has a sequential, ascending, multiple-dose design, the first patients will enter the extension study (SOBI003-002) before finalization of the FIH study. When entering the extension study, these patients will receive the highest dose that has been declared safe by the

SRC in the ongoing FIH study. Patients enrolled in Cohort 1 of FIH may thus be switched to the dose applied in Cohort 2 or Cohort 3, depending on safety clearance by the SRC. If a patient is initially switched to the dose applied in Cohort 2, the patient may subsequently later be switched to the dose applied in Cohort 3. Depending on recruitment rate in the FIH study, a patient enrolled in Cohort 1 may be directly switched to the dose applied in Cohort 3. Upon completion of the FIH study, an analysis aimed at selecting the dose for forthcoming studies will take place. Once the dose has been selected, this dose will be applied to all patients enrolled in the extension study. The Baseline in SOBI003-001 will be used as the baseline for SOBI003-002 (Figure 1).

SOBI003 is administered as weekly i.v. infusions over a period of time of 1 to 4 hours. Prior to initiation of each infusion, the patients are pretreated with a single dose of non-sedative antihistamine. If infusion-related reactions occur, then the infusion duration may be expanded up to 24 hours and supportive medication may be administered, at the discretion of the investigator.

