14.7 Other efficacy endpoints

Endpoints relating to the neurocognition, liver and spleen volume, QoL, language, motor function and sleep pattern are summarized using descriptive statistics.

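### Secondary objective 1 is a comparison of adaptive behaviour with untreated natural history patients, but the only model specified for it is one-group and cannot make that comparison

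*SAP*

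**What the plan says.** **The objective.** The protocol synopsis, protocol 6.3 and SAP 3.3 give secondary objective 1 in the same words: "To assess the effect of SOBI003 on adaptive behavior, as compared to untreated MPS IIIA patients from a NH control". The endpoint is change from baseline in VABS-II age-equivalent score (AEq) at Weeks 52 and 104.

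**The design text.** Protocol 7.1 says that "adaptive behavior data assessed in the extension study at Week 52 and Week 104 following start of treatment will be compared to available NH data"; SAP 4.1 says the same. In both, the next sentence identifies the NH comparison population as 14 rapidly progressing patients aged 12 to 72 months at baseline. Protocol 7.2 adds that, to allow comparison with the NH study, "the time points for efficacy evaluations and the neurocognitive and behavioral tools used will be identical".

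**The analysis.** SAP 14.4 states: "Adaptive behavior will be analyzed with the same repeated measures model as DQ and described in Section 14.1, but adapted for one group", and explains in parentheses that the treatment-by-visit interaction is left out. The protocol synopsis has "Adaptive behavior will be analyzed with the same repeated measures model as DQ, but adapted for one group". Protocol 9.4.4.2 agrees and names the one group as the SOBI003 group.

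**The analysis sets.** Protocol 9.2 and SAP 8.2 admit NH patients to the full analysis set with a parenthetical restriction to the DQ analyses. SAP 4.3.1 defines the control group for the DQ endpoint only.

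**The concern.** A comparative objective needs an analysis that contains the comparator. In SAP 14.1 the treatment effect on DQ is judged by the treatment-by-time term. SAP 14.4 takes the same model and removes that term, and the analysis-set definitions exclude the NH patients from this endpoint. A statistician who follows the plan to the letter will report how VABS-II AEq changed in treated children and nothing against untreated children.

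At stake is whether secondary objective 1 can be answered at all. AEq in young children moves with development and with disease progression, so change from baseline in one group does not isolate a treatment effect. If the method of comparison is settled only after results are known, in an open-label study with a caregiver-completed rating form, it will carry less weight than one fixed beforehand.

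**Working it through.** The plan gives no power, effect size, SD or NH value for VABS-II, so there is no figure to reproduce. The check sets the passages side by side.

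| Element of the comparison | Stated for adaptive behaviour? | Where |
|---|---|---|
| Intention to compare with NH | Yes | Protocol synopsis, 6.3, 7.1; SAP 3.3, 4.1 |
| Time points | Yes: Weeks 52 and 104 | Protocol 7.1; SAP 4.1 |
| Comparison population | Yes in the design text: 14 NH patients, 12 to 72 months | Protocol 7.1; SAP 4.1 |
| NH patients in the analysis set | No: limited to DQ | Protocol 9.2; SAP 8.2, 4.3.1 |
| NH VABS-II data source or values | No | – |
| Term or contrast against NH | No: interaction removed | Protocol synopsis, 9.4.4.2; SAP 14.4 |

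Count: two comparisons with NH are announced (Week 52, Week 104); none has an estimator.

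**What the model can estimate.** Let S(t) and N(t) be mean AEq at week t in SOBI003 and NH patients. The objective at Week 104 needs

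D = [S(104) − S(0)] − [N(104) − N(0)].

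In the two-group model of SAP 14.1 the treatment-by-time contrast estimates D. The one-group model estimates only the first bracket, which equals the untreated change plus any treatment effect. Without the second bracket D is not identified, and neither document supplies it. The same holds at Week 52.

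**Illustration only.** Suppose treatment has no effect and treated children change exactly as untreated children do, by c SDs of the change score, in either direction. The value of c is an assumption. Take a simple two-sided 5% one-sample t test of change against zero (df = n − 1, noncentrality c√n), with complete data and no covariates, and n at the ends of the planned 9 to 12 patients:

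| c | n = 9 | n = 12 |
|---|---|---|
| 0 | 0.05 | 0.05 |
| 0.5 | 0.263 | 0.353 |
| 1.0 | 0.748 | 0.883 |
| 1.5 | 0.975 | 0.997 |

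A between-group test under the same conditions would reject with probability 0.05 in every row. A clear one-group time effect is therefore compatible with no treatment effect. The table shows why the two quantities differ; it does not predict this trial.

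**The case against.** **The comparison is already announced.** Protocol 7.1 and SAP 4.1 give the intention, the time points, the 14 patients and their age range. This stands, and it limits the point. A reader might infer that no aspect of the comparison was fixed in advance, or that the NH patients were never linked to adaptive behaviour. The documents do not support that: the design text links them and the analysis-set text then confines them to DQ. What is missing is the data source, the estimator and the contrast.

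**Descriptive summaries may suffice.** Protocol 9.4.4.2 also says "Endpoints relating to the neurocognition, adaptive behavior, liver and spleen volume, QoL, language, motor function and sleep pattern are summarized using descriptive statistics". No such summary is stated to include NH patients. One-group estimates could be set beside published NH values, but neither the values nor a method is named.

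**The one-group model may be deliberate.** Three places agree on it, so the objective wording may be the slip. The documents do not say which. Against this, exploratory objective 1 already covers adaptive behaviour over time, so secondary objective 1 adds little without its comparator. Either way the passages conflict.

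**Unplanned analyses must be flagged.** SAP 2 and 5.2 require this in the study report. It would make an added comparison transparent, but it would not supply a prespecified method.

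**SAP 9 calls for group differences with a 95% CI.** A reader might treat the one-group model as a breach of that rule. It is a general reporting convention, which the one-group CSF HS test in SAP 14.2 does not meet either, so nothing is rested on it.

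**The endpoint carries limited weight.** It is a non-key secondary endpoint outside the testing hierarchy, in a study of 9 to 12 patients with a safety primary endpoint. This is accepted and bears on priority, not on whether the conflict exists.

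**Conclusion.** The contradiction holds. Objective 1 and the design sections promise a comparison with untreated NH patients; the specified model and analysis sets cannot deliver it. Its size is two announced comparisons without a method for one non-key secondary endpoint. It should be fixed, but it does not threaten the study's main efficacy claims: the hierarchical tests of CSF HS and DQ do not use this model.

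A reader might go further and conclude that the adaptive behaviour result will be biased. That is not supported: the documents contain no NH VABS-II values, so neither the direction nor the amount of any error can be given. Nor do they say whether patient-level NH VABS-II data are available to the sponsor. The identical behavioural tools described in protocol 7.2 suggest that a comparison was meant to be feasible, but do not settle that question.

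The conclusion rests on the wording alone. The rejection probabilities above are illustrative and depend on an assumed untreated change.

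**What to change.** Choose one route and carry it through the affected passages, preferably before database lock; the documents do not show whether lock has occurred.

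1. **Patient-level NH VABS-II data are available.** Fit the SAP 14.1 model to VABS-II AEq with the 14 NH patients and the treatment-by-time term. Report the Week 52 and Week 104 change-from-baseline contrasts with 95% CI, outside the alpha hierarchy. Name SAP 14.1 explicitly, because the DQ model in protocol 9.4.4.1 has no time-by-baseline-age term. State whether the SAP 14.1 imputation and two-week window apply. Extend the DQ-only restriction in protocol 9.2 and SAP 8.2, and the control-group definition in SAP 4.3.1, to this endpoint. Amend the one-group wording in the synopsis, protocol 9.4.4.2 and SAP 14.4.
2. **Only published NH summaries are available.** Prespecify the reference values and the method of comparison, for the population and time points already named in protocol 7.1 and SAP 4.1.
3. **Neither is available, or no comparison is wanted.** Restate objective 1 (synopsis, protocol 6.3, SAP 3.3) and the design text (protocol 7.1, SAP 4.1) as within-group change, with no comparative claim.

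The cost is wording in every case. Route 1 adds one model and needs the NH data; routes 2 and 3 need no patient-level NH data. Trial conduct and the alpha hierarchy do not change.
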